### 8.3. Analysis Populations

#### 8.3.1. Intent-to-Treat Population

The intent to treat (ITT) population for will consist of all patients who receive at least one dose of the RP2D chosen for expansion.

ITT population will be used for analyses of efficacy.

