**DOSE EXPANSION PHASE**

After completion of the Dose Escalation, Dose Expansion in up to 10 additional patients may be conducted to further explore safety, tolerability and preliminary evidence of anti-tumor activity of the RP2D of KPT-9274.

After the MTD has been established, subjects at lower dose cohorts may have the option to change dose to the MTD, per investigator discretion.

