## 2. INVESTIGATIONAL PLAN

### 2.1. Overall Study Design and Plan

This is a first-in-disease, single-center, open-label dose escalation clinical study to assess preliminary safety, tolerability, and efficacy of KPT-9274, a dual inhibitor of PAK4 and NAMPT, in patients with relapsed or refractory AML for whom all standard therapeutic options considered useful by the investigator have been exhausted.

During dose escalation, patients will receive oral KPT-9274 three times a week every other day (Days 1, 3, 5, 8, 10, 12, 15, 17, 19, 22, 24, and 26) during each 28-day cycle, and the first dose cohort will be 30 mg. Subsequent dose escalation cohorts, as well as a de-escalation cohort, will be administered per the table below. Dose escalation will continue until the MTD is determined. The MTD is defined as the highest dose at which  $\leq 1$  patient experiences a DLT in Cycle 1. A RP2D equal to or less than the MTD will be declared and used for the Dose Expansion Phase, if conducted.

Patients must complete a minimum of 1 cycle of treatment, defined as receiving  $\geq 75\%$  of KPT-9274 doses during Cycle 1 (e.g.,  $\geq 9$  of 12 doses in the 3 doses/week schedule), or have a DLT within the first cycle of treatment to be evaluable for dose escalation decisions. The cycle length is 28 days the DLT period is the first 28 days of cycle 1. Dose escalation decisions will occur when a cohort of patients has met these criteria.

After the RP2D is determined, a dose expansion phase, of up to 10 additional patients, might be conducted, in which a preliminary determination of efficacy will be conducted, using the ELN criteria (Appendix 2). After the RP2D has been established, subjects at lower dose Cohorts may have the option to change dose to the RP2D, per investigator discretion.

Screening will be performed within 30 or 14 days prior to the start of therapy (i.e., Day -30 to Day -1, or Day -14 to Day -1), as summarized in Table 1. The Follow-up period includes the EOT visit, the Safety Follow-up visit, and Durability of Response and Survival Follow-up; see Table 3 for assessments to be completed during the Follow-up period.

The number of patients required for completion of study enrollment cannot be defined *a priori* since this depends on the number of patients needed for the dose escalation; but the maximum number of patients from the escalation and expansion cohorts will be 40.

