### 4.2. Discontinuation of Study Treatment and/or Withdrawal of Patients from the Study

The Investigator may remove a patient from study treatment for any of the following reasons:

- Unacceptable AEs or toxicity that cannot be managed by supportive care
- Any medically appropriate reason (e.g., clinical progression) or significant protocol violation, in the opinion of the Investigator

The Investigator must remove a patient from study treatment for any of the following reasons:

- Disease progression per response criteria
- Patient withdraws consent to continue study treatment
- Pregnancy

Patients who are removed from study treatment by the Investigator are not permitted to restart study treatment.

Patients may discontinue study treatment for any reason. Patients who choose to discontinue study treatment will be encouraged to continue in the study so that follow-up information on disease progression and survival status may be obtained. Patients may elect to withdraw consent and decline further participation in the study at any time.

The reason for the patient's discontinuation of study treatment/withdrawal from the study must be recorded on the eCRF.

All patients will be followed until PD, withdrawal of consent, occurrence of any withdrawal criteria, intolerable toxicity precluding further treatment with study treatment, death or lost to follow up.

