## 8. STATISTICAL METHODS

### 8.1. General Considerations

Tabulations will be produced for appropriate disposition, demographic, baseline, efficacy, and safety parameters. For categorical variables, summary tabulations of the number and percentage of patients within each category (with a category for missing data) of the parameter will be presented. For continuous variables, the number of patients, mean, median, standard deviation, minimum, and maximum values will be presented. Time-to-event data will be summarized using Kaplan-Meier methodology with median event time and associated 2 sided 95% confidence intervals, as well as number and percentage of patients with events and censored patients.

Patients who are in the Dose Escalation Phase being treated at the RP2D chosen for expansion will be included in the efficacy and safety assessment of the Dose Expansion Phase.

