### 8.5. Efficacy Analysis

- **Overall response rate (AML):** complete remission (CR), complete remission with incomplete hematologic recovery (CRi), morphologic leukemia-free state (MLFS), partial remission (PR).
- **Duration of response (DOR):** the duration of time from first meeting CR, PR, MLFS, CRi, measurement criteria (whichever occurs first) until the first date that PD recurrence is objectively documented.
- **Progression-free survival (PFS):** the duration of time from date of first study treatment until the first date that PD is objectively documented or death due to any cause.
- **Overall survival (OS):** the duration of time from date of first study treatment until death from any cause.
- **Time to Progression (TTP):** The duration of time from date of first study treatment until the first date that PD is objectively documented or death due to PD. Patients without documented PD will be censored on the date of last disease assessment.

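### The efficacy population counts anyone who ever takes an RP2D dose, so patients who move up from a lower cohort bring guaranteed event-free time and lower-dose responses into the RP2D estimates

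*Combined protocol and SAP*

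**What the plan says.** - **Section 8.3.1** defines the ITT population as "all patients who receive at least one dose of the RP2D chosen for expansion" and adds that the "ITT population will be used for analyses of efficacy". There is no condition on starting dose or assigned cohort, and no other efficacy population.
- **Section 2.1** allows a later change of dose: "After the RP2D has been established, subjects at lower dose Cohorts may have the option to change dose to the RP2D, per investigator discretion". The synopsis (Dose Expansion Phase) gives the same option with a different target: "subjects at lower dose cohorts may have the option to change dose to the MTD, per investigator discretion".
- **Section 4.2** obliges the investigator to take a patient off treatment at disease progression, and states: "Patients who are removed from study treatment by the Investigator are not permitted to restart study treatment".
- **Section 8.5** measures OS as "the duration of time from date of first study treatment until death from any cause". PFS has the same origin. DOR starts at the first response, and ORR is not limited to responses first reached on the RP2D.
- **Section 8.1** pools escalation patients with the expansion: "Patients who are in the Dose Escalation Phase being treated at the RP2D chosen for expansion will be included" in its efficacy and safety assessment. It does not say whether this means the cohort assigned to that dose or anyone who later receives it.

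**The concern.** The stated objective of the expansion is preliminary efficacy at the RP2D. Under Section 8.3.1 a patient who started at a lower dose joins that analysis on taking one RP2D dose. Sections 2.1 and 4.2 together mean that only patients still alive and without documented progression can do so. Because the clock starts at first study treatment, all the time before the change is event-free by construction. This is immortal time, and it lengthens the RP2D Kaplan-Meier curves for PFS and OS even if the change of dose does nothing.

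Response is affected too. A remission first reached at the lower dose counts as an RP2D response. Under Section 6.3.1 the required end-of-cycle marrows stop once MLFS, CRi or CR is reached, so such a patient may have no required end-of-cycle marrow at the RP2D.

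The plan has no landmark, delayed entry, clock reset or separate reporting. The by-patient listings in Section 8.4 would show dose history but would not correct the summary medians.

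**Working it through.** **Plan figures.** Section 8.2.1 gives cohorts of 3 or 6 and up to 10 expansion patients. Its total reproduces: 4 × 6 + 10 = 34. The synopsis total also reproduces on its own basis: 5 × 6 + 10 = 40. Patients who start at the RP2D therefore number 3 + 10 = 13 to 6 + 10 = 16. The plan gives no expected PFS, ORR or number of dose changes, so the rest is illustration under stated assumptions.

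**Guaranteed event-free time.** A patient in the cohort just below the RP2D must pass their own 28-day DLT window and that of the RP2D cohort: 28 + 28 = 56 days. If the RP2D cohort fills as two successive groups of three, or if a higher cohort is tested and exceeds the MTD, add 28 to reach 84 days. Each further level down adds 28 more. Accrual time is extra.

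**Effect on median PFS.** Assume exponential PFS with true median *m* at every dose, no effect of changing dose, *n* starters, and *k* late entrants who change at time *c* (30.4375 days per month). The pooled curve is

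S(t) = [n·2^(−t/m) + k·g(t)] / (n + k), where g(t) = 1 before *c* and 2^(−(t−c)/m) after.

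Setting S(t) = 0.5:

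- if the solution falls before *c*: t = m·log2[2n/(n − k)];
- otherwise: t = m·log2[2(n + k·2^(c/m))/(n + k)].

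For n = 16, m = 2, c = 84 days (2.76 months): k = 1 gives 2 × log2(32/15) = 2.19 months; k = 3 gives 2 × log2(32/13) = 2.60 months. Results for n = 16, in months:

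| True median | k = 1, day 84 | k = 1, day 112 | k = 3, day 84 | k = 3, day 112 |
|---|---|---|---|---|
| 1.5 | 1.64 (+9.3%) | 1.64 (+9.3%) | 1.95 (+30.0%) | 1.95 (+30.0%) |
| 2 | 2.19 (+9.3%) | 2.19 (+9.3%) | 2.60 (+30.0%) | 2.60 (+30.0%) |
| 3 | 3.22 (+7.4%) | 3.28 (+9.3%) | 3.57 (+19.0%) | 3.83 (+27.7%) |
| 4 | 4.20 (+5.1%) | 4.30 (+7.4%) | 4.53 (+13.3%) | 4.76 (+19.0%) |

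Day 56 goes with a three-patient RP2D cohort, so n = 13. Over days 56 to 112 the ranges are then +3.8% to +11.5% (k = 1) and +9.8% to +37.9% (k = 3).

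A separate simulation (4,000 runs, 16 starters, true median 2 months) gave a mean Kaplan-Meier median of 1.9 months with no late entrants. With two it was 2.15 months (change at day 56) or 2.3 months (day 112). Across its scenarios, delayed entry or restarting the clock at the change brought the median back to within about 0.3 month of the value in starters alone.

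**How many could change.** With a 2-month median the progression-free share is 0.384 at day 84, 0.279 at day 112 and 0.203 at day 140. With three patients per lower cohort, and every progression-free patient changing, the expected numbers are:

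- RP2D at Cohort 2: 3 × 0.384 = 1.2
- RP2D at Cohort 3: 3 × (0.384 + 0.279) = 2.0
- RP2D at Cohort 4: 3 × (0.384 + 0.279 + 0.203) = 2.6

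Six-patient lower cohorts would give more: up to five of six could change, because Section 5.2.8 takes a patient with a DLT off treatment.

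**Effect on ORR.** Assume 10% response at every dose, with all lower-dose responders still progression-free at day 84. The responder share among late entrants is 0.10/0.384 = 0.26. Pooled ORR is (1.6 + 0.26k)/(16 + k): 10.9% for k = 1 and 12.5% for k = 3. These are expected values, not bounds.

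**Sampling error.** With 16 events, an approximate 95% interval around a 2-month median is 2 × exp(±1.96/√16) = 1.2 to 3.3 months.

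**The case against.** The best counter-argument is that Section 8.1 already settles the matter. It pools escalation patients who are being treated at the RP2D, which can be read as the RP2D cohort only, and the synopsis ties efficacy to the expansion portion. The sentence in 8.3.1 also has a word or phrase missing just before its criterion. On this view the fault is an ambiguity between two sections. That reading is possible, but 8.1 does not exclude patients who changed dose, and the criterion in 8.3.1 is explicit and clearly includes them.

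Other points stand as limits:

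- Both the expansion and the change of dose are optional, and there is nobody to move up if the RP2D is the lowest level treated.
- The synopsis sends patients to the MTD, which feeds this population only when the MTD and RP2D coincide.
- ORR is the primary expansion endpoint and probably moves little. If non-responders changed preferentially, it could even fall.
- No efficacy test or decision threshold depends on these estimates.
- Three late entrants at a median of 1.5 or 2 months is more than the expected number above, so 30% and 38% are the upper end. At a 4-month median, where three are readily expected (for example 3 × (0.620 + 0.529) = 3.4 with the RP2D at Cohort 3), the inflation with 16 starters is 13% to 19%.

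That the shift lies inside the confidence interval is not a defence. It always lengthens PFS and OS, and the interval does not allow for it.

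**Conclusion.** The concern holds. Followed as written, Sections 8.3.1, 2.1, 4.2 and 8.5 bias PFS and OS at the RP2D upward and mix responses from different doses. Under the assumptions above, one late entrant inflates median PFS by about 5% to 9% with 16 starters (4% to 12% with 13), and three by about 13% to 30% (10% to 38% with 13). The ORR effect is likely modest and its direction is not guaranteed. The bias requires the expansion to be run and at least one patient to move to the RP2D. It does not touch the MTD objective. It should be fixed because it is systematic, foreseeable and cheap to avoid.

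**What to change.** In Section 8.3.1, define the efficacy population as patients whose first KPT-9274 dose was the RP2D: the escalation cohort assigned to that dose plus the expansion patients. Repair the incomplete sentence at the same time. Report patients who reached the RP2D from another dose under their starting cohort, with their post-change data listed separately. Reword the pooling sentence in Section 8.1 to match. The same definition covers anyone who arrives from a higher dose.

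Separately, Section 2.1 and the synopsis name different target doses for the change (RP2D and MTD) and must be reconciled; this point takes no view on which applies.

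The cost is a few sentences in 8.1 and 8.3.1, a short descriptive listing and no new data. The RP2D efficacy table loses a few patients and keeps the 13 to 16 who started at that dose if the expansion fills.

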#### 8.3.2. Safety Population

All patients who receive any amount of the study treatment will be included in the safety population for analysis. All safety analyses will be performed on the safety population.

#### 8.3.3. DLT Evaluable Population

All patients who complete a minimum of 1 cycle of treatment, defined as having received  $\geq 75\%$  of KPT-9274 doses during Cycle 1 (e.g.,  $\geq 9$  of 12 doses in the 3 doses/week schedule), or who have a DLT within the first cycle of treatment, will be included in the DLT evaluable population.

## 8.4. Data Analysis and Presentation

Summary tabulations will be provided for disposition, demographic, baseline, efficacy and safety data as noted in the following sections. All data collected on the eCRF will be provided in by-patient data listings.

#### 8.4.1. Disposition of Patients

A tabulation of patient disposition will be presented including the number in each analysis population, the number lost to follow-up, the number that withdrew, and reason(s) for withdrawal.

#### 8.4.2. Demographic Characteristics

Demographic characteristics will be summarized by dose cohort, as well as overall, and will include date of birth, sex, race, ethnicity, and age at time of consent. For sex, race, and ethnicity, the summary statistics will be the number and percentage of patients within each category. The categories for race will be those recorded in the database. For age at time of consent, the mean, median, minimum, maximum, and standard deviation will be provided for each arm and the total sample. No formal hypothesis testing of differences among dose cohorts will be performed.

#### 8.4.3. Baseline Characteristics and Medical History

Baseline characteristics include ECOG performance status, duration from initial diagnosis, response to previous therapy, types of prior therapy, and height/weight. Baseline data will be tabulated for the same categories as used for demographics, using summary statistics; no formal hypothesis testing of dose cohort differences will be performed. Medical history and physical examination results at baseline will be tabulated by treatment cohort.

### 8.5. Efficacy Analysis

- **Overall response rate (AML):** complete remission (CR), complete remission with incomplete hematologic recovery (CRi), morphologic leukemia-free state (MLFS), partial remission (PR).
- **Duration of response (DOR):** the duration of time from first meeting CR, PR, MLFS, CRi, measurement criteria (whichever occurs first) until the first date that PD recurrence is objectively documented.
- **Progression-free survival (PFS):** the duration of time from date of first study treatment until the first date that PD is objectively documented or death due to any cause.
- **Overall survival (OS):** the duration of time from date of first study treatment until death from any cause.
- **Time to Progression (TTP):** The duration of time from date of first study treatment until the first date that PD is objectively documented or death due to PD. Patients without documented PD will be censored on the date of last disease assessment.

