***Efficacy Endpoints:***

Efficacy is an endpoint of the dose expansion portion of the study, if conducted. Bone marrow biopsies will occur for efficacy assessment purposes at the conclusion of each cycle until the subject has achieved a MLFS, CRi or CR, or per investigator discretion. Efficacy will be assessed per the European Leukemia Network guidelines.

- **Overall response rate (ORR):** complete remission (CR), complete remission with incomplete hematologic recovery (CRi), morphologic leukemia-free state (MLFS), partial remission (PR).
- **Duration of response (DOR):** the duration of time from first meeting CR, PR, MLFS, CRi, measurement criteria (whichever occurs first) until the first date that progressive disease (PD) is objectively documented.
- **Progression-free survival (PFS):** the duration of time from date of first study treatment until the first date that disease progression is objectively documented or death due to any cause.
- **Overall survival (OS):** the duration of time from date of first study treatment until death from any cause.

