Abbreviations: AE = adverse event; CBC = complete blood count; D = Day; ECG = electrocardiogram; ECOG = Eastern Cooperative Oncology Group; EoT = End of Treatment

Sites should adhere to the 28-day cycle.

 Vital signs: blood pressure, pulse and body temperature; see Section 6.4.1.2 for a detailed description of vital sign assessments.

 Complete metabolic panel (CMP) equals: sodium, potassium, chloride, carbon dioxide, glucose, blood urea nitrogen, creatinine, magnesium, phosphorous, uric acid, alkaline phosphatase, alanine aminotransferase, aspartate aminotransferase, bilirubin, protein, albumin and lactate dehydrogenase

 BM - day 28 +/- 3 days; conclusion of each cycle until the subject has achieved a MLFS, CRi or CR, or per investigator discretion

[name]  
IRB # 20-2350

KPT-9274

**Table 3** Schedule of Assessments: End-of-Treatment and Beyond

Activity/Assessment	End-of-Treatment (EoT) Visit	Safety Follow-up 	Durability of Response and Survival Follow-up
	≤ 14 Days Post Last Dose	30 Days Post-Last Dose	Every 3 months for 1 year after the safety follow-up call
		+ 7 days	± 7 days
Clinical Assessments			
Patient weight	X		
Vital Signs (BP, pulse, temp) 	X		
Complete physical exam	X		
ECOG	X		
Bone marrow biopsy, if not performed <30 days prior to EoT	X		
Clinical Labs			
CBC with differential	X		
Complete metabolic panel 	X		
Serum hCG pregnancy test	X		
Adverse events	X	X	
Concomitant medications	X	X	
Survival and Response Status			X

Abbreviations: AE = adverse event; CBC = complete blood count; D = Day; ECG = electrocardiogram; ECOG = Eastern Cooperative Oncology Group; EoT = End of Treatment.

Sites should adhere to the 28-day cycle.

 Vital signs: blood pressure, pulse and body temperature; see Section 6.4.1.2 for a detailed description of vital sign assessments.

2 Complete metabolic panel (CMP) equals: sodium, potassium, chloride, carbon dioxide, glucose, blood urea nitrogen, creatinine, magnesium, phosphorous, uric acid, alkaline phosphatase, alanine aminotransferase, aspartate aminotransferase, bilirubin, protein, albumin and lactate dehydrogenase

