### **5.7.3. Prohibited Concomitant Medications**

The use of niacin or niacin-containing supplements (e.g., multivitamins and energy drinks) is not allowed. Investigational or commercial anticancer agents other than KPT-9274 are not allowed during the study. The initiation of any non-protocol specific anti-tumor treatment is considered an indication of disease relapse/progression and should be recorded appropriately in the eCRFs.

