## 6.3. Efficacy Assessments

#### 6.3.1. Bone Marrow Aspirate and Biopsy

Bone marrow biopsy and aspirate will be taken within 30 days prior to first dose (baseline) for all AML patients. This will be repeated on cycle 1 day 8. It will again be repeated, for efficacy purposes according to the ELN criteria, at the conclusion of each cycle until the subject has achieved a MLFS, CRi or CR, or per investigator discretion. . It will also be performed as an end of treatment assessment if this occurs >30 days from another scheduled or unscheduled bone marrow biopsy. Bone marrow biopsies will also be performed at any time at the discretion of the investigator in accordance with standard of care (i.e. at the time of suspected progression, etc).

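### Duration of response has no death event: a responder who dies without documented PD is a non-event, and the Kaplan-Meier median is overstated if such deaths are censored at or near death

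*Combined protocol and SAP*

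**What the plan says.** DOR is defined in three places. The Synopsis (Efficacy Endpoints) and Section 2.2.2 measure it from first response "until the first date that progressive disease (PD) is objectively documented". Section 8.5 measures it "until the first date that PD recurrence is objectively documented". None of the three names death.

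The neighbouring endpoints in Section 8.5 do. PFS runs "until the first date that PD is objectively documented or death due to any cause". Time to progression (TTP) counts PD or a death caused by PD, and carries the only censoring rule in the list: "Patients without documented PD will be censored on the date of last disease assessment". DOR has no such sentence.

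Section 8.1 sets the estimator: "Time-to-event data will be summarized using Kaplan-Meier methodology with median event time and associated 2 sided 95% confidence intervals". It also promises counts of events and of censored patients, without saying who is censored for DOR or on what date.

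On assessments, Section 6.3.1 schedules marrows "at the conclusion of each cycle until the subject has achieved a MLFS, CRi or CR, or per investigator discretion". It adds an end-of-treatment marrow when more than 30 days have passed since another one, and marrows at suspected progression. Section 6.3.2 ties response assessment to each marrow from Cycle 1 Day 28. Table 3 adds survival and response-status follow-up "Every 3 months for 1 year after the safety follow-up call".

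**The concern.** A reader will take DOR as time spent alive and in response. On that meaning death ends the response, yet the written definition does not treat it as an end. Even a death due to PD, if PD was never documented beforehand, is an event for TTP and a non-event for DOR.

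Kaplan-Meier treats a censored responder as someone who would go on to relapse at the same rate as those still followed. A responder who has died will not. Censoring the death at or near its date removes a failure from the curve while keeping the response time before it, so the curve sits too high and the median is too long. At stake is how durable responses at the RP2D appear in a report based on few responders.

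**Working it through.** The plan states no DOR median, rate or event count, so there is no figure of its own to reproduce. The check is on direction and on size over an assumed range.

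**Inputs**
- Event definitions: Sections 2.2.2 and 8.5 and the Synopsis. Estimator: Section 8.1.
- Assumed, not in the documents: constant hazards, L1 for documented PD and L2 for death without documented PD. The share of response endings that are such deaths is d = L2/(L1+L2), set at 10%, 20% and 40%.

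**Step 1. Deaths censored at the death date**
- Median with deaths censored: ln 2 / L1.
- Median with death as an event: ln 2 / (L1+L2).
- Ratio: (L1+L2)/L1 = 1/(1-d).
- d = 10%: 1/0.9 = 1.11. d = 20%: 1/0.8 = 1.25. d = 40%: 1/0.6 = 1.67.

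The ratio does not depend on the median itself. For illustration, a reported median of 4.0 months would correspond to 4.0 × 0.9 = 3.6, 4.0 × 0.8 = 3.2 and 4.0 × 0.6 = 2.4 months alive in response. At the true median, where the curve should read 0.50, it reads 0.5^(1-d) = 0.536, 0.574 and 0.660.

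**Step 2. Deaths censored near death**

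Here a death is censored at the last 3-monthly contact before it. With an assumed true median of 6 months, simulation of 400,000 responders gives ratios of 1.09, 1.21 and 1.56. For a true median of 3 months they are 1.08, 1.17 and 1.45; for 12 months, 1.10, 1.23 and 1.61. Most of the overstatement remains.

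**Step 3. Deaths censored much earlier**

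If deaths alone are moved back to the response date and there is no other censoring, the ratio is 1.00: those patients leave the risk set at time zero and, under constant hazards, the rest are unchanged. So the size of the bias depends on a censoring date that the plan does not give.

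**Step 4. Hand example**

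Five responses end at months 1, 2, 3, 4 and 5.
- All are events: S = 0.8, 0.6, 0.4, so the median is 3.
- The month-3 ending is a death without PD, censored at death: S(2) = 0.6 and S(4) = 0.6 × 1/2 = 0.30, so the median is 4.
- The same death is censored at the response date: S(1) = 0.75 and S(2) = 0.50, so the median is 2.

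One patient's handling moves the median from 3 to 4 or to 2.

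**The case against.** **A PD-only DOR can be legitimate.** It can be read as a cause-specific quantity, with death as a competing event. That is fair, but the plan neither labels it so nor plans a competing-risk summary such as cumulative incidence. A Kaplan-Meier median with deaths censored will be read as time in response.

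**The plan does not say that deaths are censored at death.** This stands. A reader might infer that reported DOR will be overstated whatever is done; the documents do not support that. If the TTP rule were borrowed, the censoring date could be earlier and the bias smaller.

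**Scheduled marrows stop at MLFS, CRi or CR.** A reader might infer that censoring would fall at the response date and make DOR too short. If every non-event were censored there, with 12 months of follow-up and a true median of 6 months, the ratio would be 0.68. That is an extreme case rather than the documented schedule: Section 6.3.1 keeps marrows at end of treatment and at suspected progression, and patients in PR continue with a marrow each cycle.

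**The weight is limited.** This also stands. DOR is secondary in an expansion of up to 10 added patients that may not take place, with no hypothesis test. The same deaths count in PFS and OS, and Section 8.6.1 lists deaths by patient.

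**Conclusion.** The point holds in conditional form. The written definition leaves a responder's death without documented PD as a non-event in all three places. When such deaths are censored at or near death, the Kaplan-Meier median exceeds the median time alive in response by 1/(1-d): 1.11, 1.25 or 1.67 for d of 10%, 20% or 40%. This rests on constant hazards, on assumed shares, and on DOR meaning time alive in response. No frequency of affected trials is claimed, since that would depend on an unknown number of responders and on length of follow-up.

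A reader might infer that the efficacy conclusion or the dose choice is compromised. It is not: MTD and RP2D do not use DOR, ORR is counted without it, and PFS and OS already include these deaths. The plan should be corrected, but the consequence is confined to one descriptive secondary estimate.

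**What to change.** In the Synopsis, Section 2.2.2 and Section 8.5, use one definition: DOR ends at documented relapse or PD or at death from any cause, whichever comes first. Censor responders with neither at the last disease assessment.

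Define that term. Section 6.3.2 places response assessment at each marrow, while Table 3 collects response status at 3-monthly contacts for which it lists no CBC or marrow. The definition should say whether those contacts count, and Section 6.3.2 should agree with it.

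The cost is text plus that one decision; no visit is added, and deaths are already collected. The downside is that DOR will probably be shorter and less favourable than with deaths censored at death.

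Three related matters do not carry this point and should be raised separately:
- PFS and OS have no stated censoring rules.
- Section 5.7.3 says "The initiation of any non-protocol specific anti-tumor treatment is considered an indication of disease relapse/progression", whereas DOR requires objective documentation; the two need reconciling.
- Sections 4.2 and 5.2.8 need reconciling with Table 3, Section 2.1 and Table 7 on whether stopping treatment also ends follow-up.
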